- In Sequence A, if one hypothesis is not rejected at alpha level of 2.5% then no statistically significant will be claimed for any subsequent hypotheses in the sequence. In this case, the assessing for statistical significance in Sequence B will be at the 2.5% level. If all hypotheses in Sequence B are rejected, then the unused alpha level of 2.5% will be passed back for assessing the hypotheses in Sequence A at the 5% level. In Sequence B, if one hypothesis is not rejected at alpha level of 2.5 % then no statistically significant will be claimed for any subsequent hypotheses in the sequence.

Figure 2 Schematic for Multiple Testing Procedure

The figure above illustrates the procedure showing the sequence of the tests.

In order to be more rigorous about the onset of relief of severity of pruritus, a step-down approach with the NRS4 endpoint from Week 2 to earlier time points will be utilized as an additional family of hypothesis tests separate from [Figure 2](#) once statistical significance is demonstrated at Week 2. Rejection of each hypothesis of no difference in NRS4 at Week 2 within Sequence A will enable further assessing at earlier time points. Specifically, further hypotheses of no difference in NRS4 will be assessed along the following four sequences:

- If hypothesis of no difference in NRS4 at Week 2 between 200 mg QD and placebo is rejected in Sequence A, compare 200 mg QD versus placebo at Day 15, Day 14, Day 13, Day 12, ..., Day 2, in that order. Any hypotheses after the last time point (or Day) for which the comparison 200 mg QD versus placebo is significant will not be considered statistically significant.
- If hypothesis of no difference in NRS4 at Week 2 between 100 mg QD and placebo is rejected in Sequence A, compare 100 mg QD versus placebo at Day 15, Day 14, Day 13, Day 12, ..., Day 2, in that order. In this sequence, any hypotheses after the last time point (or Day) for which both comparisons (200 mg QD versus placebo and 100 mg QD versus placebo) are significant will not be considered significant.
- If hypothesis of no difference in NRS4 at Week 2 between 200 mg QD and dupilumab is rejected in Sequence A, compare 200 mg QD versus dupilumab at Day 15, Day 14, Day 13, Day 12, ..., Day 2, in that order. For this sequence, any hypotheses after the last time point (or Day) for which both comparisons (200 mg QD versus placebo and 200 mg QD versus dupilumab) are significant will not be considered significant.

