- If hypothesis of no difference in NRS4 at Week 2 between 100 mg QD and dupilumab is rejected in Sequence A, compare 100 mg QD versus dupilumab at Day 15, Day 14, Day 13, Day 12, ..., Day 2, in that order. For this sequence, any hypotheses after the last time point (or Day) for which all four comparisons (200 mg QD versus placebo, 200 mg QD versus dupilumab, 100 mg QD versus placebo and 100 mg QD versus dupilumab) are significant will not be considered significant.

All hypotheses in each of the four sequences will be assessed at the 5% level of significance. Although this testing procedure will not protect the Type-I error for the family of all possible comparisons, it will provide Type-I error protection for the family of NRS4 time points within each treatment group and treatment groups within each time point.

Hypotheses corresponding to all secondary and other endpoints will be tested at the 5% level of significance without any adjustment for multiplicity.

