5.2. General Methods

In general, for descriptive analyses, number and percent will be presented for binary variables. Number, mean, standard deviation, median, first and third quartiles will be presented for continuous variables.

Estimates of the pairwise differences along with its two-sided 95% confidence interval will be provided among the treatment groups, PF-04965842 200 mg QD, PF-04965842 100 mg QD, dupilumab and placebo. No statistical significance will be claimed unless an exception is noted in [Section 5.1](#) or [Section 6](#) or any of its subsections.

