5.2.1. Analyses for Binary Data

Binary data at each scheduled visit will be analyzed by two approaches: (1) the test of hypothesis (and the p-value) of no difference between two treatment groups will be conducted by the Cochran-Mantel-Haenszel (CMH) statistic adjusting for baseline disease severity (moderate or severe); p-values from the CMH statistic will be used to test the hypothesis of no difference in binary responses between two treatment groups; and (2) the proportion of responders in each treatment group will be reported and differences between two treatment groups will be summarized by the weighted difference and its 95% confidence interval obtained by normal approximation. The difference in proportions will be calculated within each randomization stratum. The final estimate of the difference in proportions will be a weighted average of these stratum-specific estimates using CMH weights. The CMH weight w_k for stratum k ($k = 1, 2$) is given by,

$$w_k = \frac{\frac{n_{ik} n_{ck}}{n_{ik} + n_{ck}}}{\sum_{j=1}^2 \frac{n_{ij} n_{cj}}{n_{ij} + n_{cj}}}$$

where n refers to sample size, the subscript c refers to a comparator group (eg, placebo) and the subscript i refers to a test group (eg, an active treatment group). The difference is estimated as $\hat{d} = \sum_{k=1}^2 w_k (\hat{p}_{ik} - \hat{p}_{ck})$, where \hat{p} refers to the estimated proportion. An estimate for \hat{p} is obtained as x/n , where x is the number of responders.

Two-sided 95% confidence intervals for the difference (based on a normal approximation) are formed by:

$$\hat{d} \pm 1.96 \sqrt{\sum_{k=1}^2 w_k^2 \left(\frac{\hat{p}_{ik}(1 - \hat{p}_{ik})}{n_{ik}} + \frac{\hat{p}_{ck}(1 - \hat{p}_{ck})}{n_{ck}} \right)}$$

In the above formula, the standard error is $\sqrt{\sum_{k=1}^2 w_k^2 \left(\frac{\hat{p}_{ik}(1 - \hat{p}_{ik})}{n_{ik}} + \frac{\hat{p}_{ck}(1 - \hat{p}_{ck})}{n_{ck}} \right)}$. When the number of responders is zero ($x = 0$), then \hat{p} will be replaced by $0.5/(n + 1)$.

The 95% confidence interval for the response rate in each treatment group will also be provided using Wald normal approximation (or the Clopper-Pearson exact method when there are no or all responders in one group).

090177e1937d0b4eApproved\Approved On: 18-May-2020 15:17 (GMT)

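### SAP 5.1 claims more Type I error protection for the daily NRS4 step-down than the procedure gives once both comparators are counted

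*SAP*

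**What the plan says.** SAP 5.1 adds a family of daily NRS4 tests, separate from the main testing procedure (Figure 2), to locate the onset of itch relief. Rejection at Week 2 within Sequence A opens the matching daily sequence, which runs from Day 15 back to Day 2. The same-day gates are:

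- 200 mg versus placebo: its own earlier steps only.
- 100 mg versus placebo: nothing counts past the last day on which "both comparisons (200 mg QD versus placebo and 100 mg QD versus placebo) are significant will not be considered significant".
- 200 mg versus dupilumab: nothing counts past the last day on which "both comparisons (200 mg QD versus placebo and 200 mg QD versus dupilumab) are significant will not be considered significant".
- 100 mg versus dupilumab: requires "all four comparisons (200 mg QD versus placebo, 200 mg QD versus dupilumab, 100 mg QD versus placebo and 100 mg QD versus dupilumab").

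There is no split of alpha: "All hypotheses in each of the four sequences will be assessed at the 5% level of significance". The closing sentence starts with a disclaimer, "Although this testing procedure will not protect the Type-I error for the family of all possible comparisons", and then asserts that "it will provide Type-I error protection for the family of NRS4 time points within each treatment group and treatment groups within each time point".

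SAP 5.2 adds that "No statistical significance will be claimed unless an exception is noted in" Section 5.1 or Section 6. SAP 6 and 6.4.1 plan p-values against dupilumab for Days 2 to 15.

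**The concern.** A series of tests at 5%, each opened only by rejection of the one before, keeps the familywise error at 5%. Here the series splits in two. After 200 mg beats placebo on a given day, two further tests open together, each at a full 5%, and neither waits for the other. The same happens over time: once 200 mg versus dupilumab stops, 200 mg versus placebo carries on at 5%. A true null on each branch gives two chances of a false rejection inside a family that the sentence describes as protected.

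What is at stake is the accuracy of a stated property. A reader judging a claim about the first day of itch relief would look to this sentence to learn how the claim is controlled.

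**Working it through.** **Inputs.** Two-sided 5% per daily test (SAP 2.2 and 5.1). Arms of 200, 200, 200 and 100 for 200 mg, 100 mg, dupilumab and pooled placebo (SAP 2.2). Pairwise tests "conducted by the Cochran-Mantel-Haenszel (CMH) statistic adjusting for baseline disease severity (moderate or severe") (SAP 5.2.1), so each uses only the two arms compared. Planned dupilumab NRS4 rate of 18% at Week 2, with a 15-point difference (SAP 2.2). Phase 2b Day 15 rates of 69.8%, 41.1% and 15.7% for 200 mg, 100 mg and placebo (Protocol 1.2.4). The documents give no daily rates before Day 15, so all early-day rates below are assumptions. I read each sequence as stopping at its first non-significant day.

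**Calibration.** The SAP gives no familywise figure for the daily tests, so I checked the arm sizes on its NRS4 power. For 33% versus 18%, 200 per arm: [0.15 - 1.96 x sqrt(2 x 0.255 x 0.745/200)] / sqrt(0.18 x 0.82/200 + 0.33 x 0.67/200) = (0.15 - 0.0854)/0.0429 = 1.50. This gives 93.4% (91.7% with continuity correction) against the stated 92%.

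**Within a day, worst case.** Let 200 mg clearly beat placebo, 100 mg equal placebo and 200 mg equal dupilumab. Both open nulls are true, and the two tests share no arm, so they are independent.

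- Two-sided: 1 - 0.95 x 0.95 = 9.75%.
- In favour of PF-04965842: 1 - 0.975 x 0.975 = 4.94%, against 2.5% for one test.

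Of all 15 patterns of equality among the four arms, this was the only one above 5% (simulated 9.6%). Every other pattern gave 5.0% or less. Within a day, therefore, the two doses against one comparator are protected, and so is one dose against both comparators.

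**Within a day, finite rates.** Exact binomial enumeration, one day, pooled z tests, no gate other than 200 mg versus placebo, 100 mg = placebo = 15.7%:

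| 200 mg = dupilumab | Gate passed | Two-sided error | In favour of PF-04965842 |
|---|---|---|---|
| 18% | 6.6% | 1.9% | 1.9% |
| 25% | 45.5% | 4.5% | 4.2% |
| 33% | 91.1% | 7.5% | 4.7% |
| 40% | 99.5% | 9.3% | 4.7% |

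The two-sided error passes 5% at about 27%. With placebo at 5% (assumed) and dupilumab at 18%, it is 7.4%. A CMH version with assumed strata (60% moderate, severe-stratum odds ratio 0.6) gives 1.9/4.5/7.4/9.5% for the four rows.

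**Within a day, all gates included.** These runs add the Week 2 gate at 2.5% and every day from Day 15 down to Day 10 or Day 5. They assume the Sequence A order, because Figure 2 is not shown, and an adjacent-day correlation of 0.9, or 0.98 in some gradual-onset runs.

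- Phase 2b Week 2 rates, abrupt separation: 1.8-2.0/4.6/7.3-7.5/8.9-9.2% at 18/25/33/40%.
- Phase 2b Week 2 rates, gradual (linear) separation: 1.0 to 4.9%.
- Planned Week 2 rates (33% versus 18 to 25%): at most 2.8%.
- Placebo 5% on early days, dupilumab 18%: abrupt 7.1 to 7.6%, gradual 2.8 to 4.1%.

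**Within a dose, across days.** Let 200 mg equal dupilumab at Day 10 and equal placebo at Day 5. The Day 10 test against dupilumab depends on 200 mg versus placebo only down to Day 10, where that difference is real. The Day 5 test against placebo never depends on dupilumab. Each null is therefore tested at 5%, and the bound is 5% + 5% = 10%. The tests share the 200 mg arm, so the error falls somewhat below that bound. A simulation used 20,000 replicates, adjacent-day correlation 0.9 to 0.98 and abrupt onset. For example, 200 mg is at 69.8% down to Day 11, 200 mg = dupilumab = 25% for Days 10 to 6, and 200 mg = placebo = 5% at Day 5, with placebo at 5% throughout. The result is about 9.4 to 9.5%. In the cases tried, linear separation stayed below 5%. Planned Week 2 rates also did with placebo at 15.7%, but abrupt onset with placebo at 5% brought them marginally over.

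**The case against.** The strongest reply is about reading. The sentence opens by disclaiming all possible comparisons, and if both halves are read per comparator they are true. That is fair as far as it goes. But the SAP states no such limit, and its own gates cross comparators: 200 mg versus dupilumab waits for 200 mg versus placebo, and 100 mg versus dupilumab waits for everything. Pooling the comparators is the natural reading.

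Three further objections stand and set the size of the point.

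- The excess needs exact equalities, abrupt onset, and either rates above plan or a low placebo rate.
- The daily tests are secondary (SAP 6.4.1), SAP 5.1 tests other secondary endpoints at 5% without adjustment, and no passage plans a pooled claim on the unprotected comparisons.
- SAP 5.2 says where significance may be claimed. It does not itself define error control.

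A reader might go further and infer that the trial's overall familywise error is near 10%. The documents do not support this: the daily family is separate from the main procedure, and its results pass no alpha back. Nor can it be inferred that, within a day, false claims favouring PF-04965842 exceed 5%. Their worst case is 4.94%, which is twice the 2.5% of a single test but still below 5%. A narrower inference, that one same-day pair is the only gap, also fails, because the across-day half has the same fork.

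**Conclusion.** The sentence is wrong as written, and the point is minor. It is true for one dose against one comparator across days. Within a day it is true for the two doses against one comparator and for one dose against both. It is not true within a day for 100 mg versus placebo together with 200 mg versus dupilumab (worst case 9.75% two-sided), nor for one dose across days with both comparators counted (about 9.4 to 9.5% simulated, bound 10%).

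The two figures differ in standing. The 9.75% follows from the gates and the 5% level alone, when the earlier gates pass with near certainty. The across-day figure rests on assumed daily rates, correlation and abrupt onset. The reassurance below 5% is conditional too: it holds with gradual onset, or at the planned Week 2 rates with placebo near 15.7%. The full-sequence results also rest on an assumed Sequence A order. None of this touches the co-primary or key secondary tests.

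**What to change.** Keep every test and replace the sentence with, for example:

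> Type I error is protected at 5% across time points for each dose versus a given comparator and, within a time point, for the two doses versus a given comparator and for a given dose across both comparators. It is not protected jointly across both comparators over time points, nor within a time point for 100 mg versus placebo together with 200 mg versus dupilumab, where the two-sided error can approach 10%.

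The cost is one or two sentences. No test, estimate or power figure changes.

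Testing 100 mg versus placebo and 200 mg versus dupilumab at 2.5% each would not rescue the present sentence. It brings the same-day pair to 1 - 0.975^2 = 4.94%. Across days, 200 mg versus placebo would still be at 5% and 200 mg versus dupilumab at 2.5%, so the error could reach about 1 - 0.95 x 0.975 = 7.4% (about 6.9 to 7.0% simulated). It would also contradict the neighbouring statement that every hypothesis is assessed at 5%.

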5.2. General Methods

In general, for descriptive analyses, number and percent will be presented for binary variables. Number, mean, standard deviation, median, first and third quartiles will be presented for continuous variables.

Estimates of the pairwise differences along with its two-sided 95% confidence interval will be provided among the treatment groups, PF-04965842 200 mg QD, PF-04965842 100 mg QD, dupilumab and placebo. No statistical significance will be claimed unless an exception is noted in [Section 5.1](#) or [Section 6](#) or any of its subsections.

5.2.1. Analyses for Binary Data

Binary data at each scheduled visit will be analyzed by two approaches: (1) the test of hypothesis (and the p-value) of no difference between two treatment groups will be conducted by the Cochran-Mantel-Haenszel (CMH) statistic adjusting for baseline disease severity (moderate or severe); p-values from the CMH statistic will be used to test the hypothesis of no difference in binary responses between two treatment groups; and (2) the proportion of responders in each treatment group will be reported and differences between two treatment groups will be summarized by the weighted difference and its 95% confidence interval obtained by normal approximation. The difference in proportions will be calculated within each randomization stratum. The final estimate of the difference in proportions will be a weighted average of these stratum-specific estimates using CMH weights. The CMH weight w_k for stratum k ($k = 1, 2$) is given by,

$$w_k = \frac{\frac{n_{ik} n_{ck}}{n_{ik} + n_{ck}}}{\sum_{j=1}^2 \frac{n_{ij} n_{cj}}{n_{ij} + n_{cj}}}$$

where n refers to sample size, the subscript c refers to a comparator group (eg, placebo) and the subscript i refers to a test group (eg, an active treatment group). The difference is estimated as $\hat{d} = \sum_{k=1}^2 w_k (\hat{p}_{ik} - \hat{p}_{ck})$, where \hat{p} refers to the estimated proportion. An estimate for \hat{p} is obtained as x/n , where x is the number of responders.

Two-sided 95% confidence intervals for the difference (based on a normal approximation) are formed by:

$$\hat{d} \pm 1.96 \sqrt{\sum_{k=1}^2 w_k^2 \left(\frac{\hat{p}_{ik}(1 - \hat{p}_{ik})}{n_{ik}} + \frac{\hat{p}_{ck}(1 - \hat{p}_{ck})}{n_{ck}} \right)}$$

In the above formula, the standard error is $\sqrt{\sum_{k=1}^2 w_k^2 \left(\frac{\hat{p}_{ik}(1 - \hat{p}_{ik})}{n_{ik}} + \frac{\hat{p}_{ck}(1 - \hat{p}_{ck})}{n_{ck}} \right)}$. When the number of responders is zero ($x = 0$), then \hat{p} will be replaced by $0.5/(n + 1)$.

The 95% confidence interval for the response rate in each treatment group will also be provided using Wald normal approximation (or the Clopper-Pearson exact method when there are no or all responders in one group).

090177e1937d0b4eApproved\Approved On: 18-May-2020 15:17 (GMT)

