5.2.6. Analyses of Tier-1 and Tier-2 Events

Number and percentage of subjects with AEs over the duration of treatment will be provided for each treatment group. Tier-1 events will be analyzed using methods proposed by Chan and Zhang (1999). Tier-2 events will be analyzed using asymptotic methods proposed by Miettinen and Nurminen (1985). Risk differences (each PF-04965842 dose group compared to placebo, and each PF-04965842 dose group compared to dupilumab) and 2-sided 95% confidence intervals will be reported. P-values will also be reported for Tier-1 events. Tier-3 events will not be summarized separately but included within the summary of all AEs.

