6.7. Subset Analyses

Summary statistics for co-primary endpoints will be presented by subgroups below.

- Age (years) group (<40, ≥40; <65, ≥65);
- Sex (Male, Female);
- Race (White, Black or African-American, Asian, Other²);
- Region of enrollment (US/Canada/Australia, Europe, Asia, Latin America);
- Weight (kg) (less than or equal to the median value in FAS, above the median value);
- AD Duration (years) group (<26, ≥26);
- Baseline disease severity (moderate, severe);
- Baseline EASI group (16-25, >25);
- Baseline % BSA group (10-30, >30-50, >50);
- Previous use of systemic immunosuppressant for AD (Yes, No).

Estimates of the response of and all pairwise difference between the PF-04965842 200 mg QD, PF-04965842 100 mg QD and placebo, along with the 95% confidence interval (no p-value), will be presented for each defined category of each subgroup. For the binary endpoints, analyses will be performed using normal approximation without any adjustments for baseline disease severity.

The primary purpose of the subgroup analyses is to check for consistency of results across subgroups, to make sure overall results are not being driven by some subset of subjects.

Graphical display (eg, forest plots) of the differences between treatment groups will be presented. There is no intention to have any specific inference within subgroups.

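### SAP 5.2.1 does not limit its zero-responder substitution to the standard error, and it has no matching rule for the interval of a difference when every subject in an arm responds

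*SAP*

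**What the plan says.** SAP 5.2.1 uses a single symbol, p-hat, which "is obtained as x/n , where x is the number of responders". It enters the stratum-specific differences and the standard error. For the pooled result, "The final estimate of the difference in proportions will be a weighted average of these stratum-specific estimates using CMH weights".

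Directly after the standard error formula comes the boundary rule: "When the number of responders is zero ($x = 0$), then" p-hat "will be replaced by $0.5/(n + 1"), that is, by half a responder over n + 1. The sentence does not say whether this applies to the difference, to the standard error, or to both. It has no counterpart for x = n.

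Three other provisions bear on the point:

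- Tests do not use the substituted value: "p-values from the CMH statistic will be used to test the hypothesis of no difference in binary responses between two treatment groups".
- The interval for each arm's own response rate is Wald, "or the Clopper-Pearson exact method when there are no or all responders in one group". Both boundaries are therefore covered there, but only for that interval.
- For subgroups of the co-primary endpoints, SAP 6.7 states that "analyses will be performed using normal approximation without any adjustments for baseline disease severity". It does not say whether the zero rule carries over.

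**The concern.** A boundary correction is normally there to stop the standard error collapsing to zero. If it also replaces the estimate, the reported difference depends on how many subjects were in each empty arm. With 2:1 allocation against placebo, an empty placebo arm receives about twice the value of an empty PF-04965842 arm, so two arms with no responders show a negative difference. A table could then list 0% and 0% beside a non-zero difference.

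The other boundary is unprotected. When all subjects in an arm respond, p-hat(1 - p-hat) is zero and that arm adds nothing to the variance of the difference.

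At stake are the reported differences and 95% intervals for rare or early endpoints (for example EASI-100, or NRS4 in the first days) and for small subgroups in the co-primary forest plots, whose stated purpose is to check consistency. Two programmers could also code the sentence differently and both claim to follow the SAP.

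**Working it through.** **Inputs.** Arm sizes are 200, 200, 200 and 100 (placebo sequences pooled), from SAP 2.2. Planning rates from the same section are 12% versus 32% for IGA and 23% versus 53% for EASI-75. The formulas for the weights, difference and standard error are in SAP 5.2.1. The severity split, low true rates and subgroup sizes are assumptions, because the documents do not give them. The SAP gives no worked figure for the zero rule, so there is none to reproduce.

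**1. Both arms empty, one stratum, rule applied everywhere.** d = 0.5/201 - 0.5/101 = 0.249% - 0.495% = -0.25 point. SE = 0.785 point; 95% CI -1.79 to +1.29. With the rule in the standard error only, d = 0 and the CI is -1.54 to +1.54.

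**2. The same, by stratum.** Assume 65% moderate, giving 130/65 and 70/35. The CMH weights are then 0.65 and 0.35.

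- Moderate: 0.5/131 - 0.5/66 = -0.376 point.
- Severe: 0.5/71 - 0.5/36 = -0.685 point.
- Weighted: 0.65 x (-0.376) + 0.35 x (-0.685) = -0.48 point.

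With the moderate share between 50% and 80%, the result stays between -0.478 and -0.485 point, with a CI of about -2.6 to +1.7.

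**3. Average bias when the true rates are equal and low (same split).** Bias = sum over strata of w x [0.5/(ni+1) x (1-p)^ni - 0.5/(nc+1) x (1-p)^nc]. This gives -0.46 point at p = 0.5%, -0.41 at 1% and -0.29 at 2%.

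**4. A small effect with an empty placebo arm.** Take 2/130 and 1/70 versus 0/65 and 0/35. The observed weighted difference is 0.65 x 1.538 + 0.35 x 1.429 = 1.5 points. The literal rule gives 0.65 x (1.538 - 0.758) + 0.35 x (1.429 - 1.389) = 0.52 point.

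**5. Subgroups.** An empty placebo subgroup of 2, 3, 5, 10 or 20 subjects would be assigned 16.7%, 12.5%, 8.3%, 4.5% or 2.4%. For an assumed 3/10 versus 0/5:

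| Reading | Difference (points) | 95% CI |
|---|---|---|
| No rule in subgroups | 30.0 | 1.6 to 58.4 |
| Rule applied everywhere | 21.7 | -15.7 to 59.0 |
| Rule in the SE only | 30.0 | -7.3 to 67.3 |

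Without any rule, the empty placebo arm has zero variance and the interval excludes 0. At the 12% planning rate for IGA, an empty placebo subgroup has probability 0.88^5 = 53% for n = 5 and 0.88^10 = 28% for n = 10.

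**6. All responders.** 10/10 versus 5/5 gives d = 0, SE = 0 and CI [0, 0]. For 10/10 versus 2/5, SE = sqrt(0.4 x 0.6/5) = 21.9 points, all from the placebo arm. With (n+0.5)/(n+1) in the standard error only, 10/10 versus 5/5 keeps d = 0 but has SE 14.0 points, so the interval is about 0 ± 27.5.

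**7. What does not move.** A dose versus dupilumab at 0/200 each gives 0.5/201 - 0.5/201 = 0. The CMH test works from counts. An empty placebo arm of 100 at a 12% rate has probability 0.88^100 = 0.0003%.

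**The case against.** The strongest reply is positional. The zero-responder sentence follows immediately on the standard error, so it can be read as a repair to that formula alone. The Clopper-Pearson provision, which still treats an empty arm as 0/n, fits that reading. On it, the negative difference and the shrunken subgroup effect both disappear from the point estimate. This stands as an open reading but does not settle the matter, since the wording replaces the symbol used in both places.

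The reply on size also largely stands. The headline shift is a quarter to half a point, with an interval that includes 0. When placebo is the empty arm, the shift works against the study drug. SAP 6.7 disclaims inference within subgroups and presents no p-values. At the planning rates, 0/10 versus 0/5 has probability 0.68^10 x 0.88^5 = about 1.1% for IGA. An all-responder arm is uncommon too: at 53%, a group of 5 gives 0.53^5 = about 4%.

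A reader might infer more than the documents support:

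- That the trial will report a negative effect for 0/200 versus 0/100. This requires the literal reading, and the text is ambiguous.
- That placebo responders are being invented. The substitution is a half-responder correction that applies equally to an empty active arm.
- That zero cells are to be expected early in the severe stratum. The documents give no early IGA, EASI-90 or EASI-100 rates for this trial and no severe share.

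**Conclusion.** The point holds as a minor defect in reported estimates and intervals. As worded, SAP 5.2.1 allows the substitution to enter the difference. Against placebo, that turns 0/200 versus 0/100 into about -0.25 point, or about -0.5 point by stratum. If the rule carries over to subgroups, it turns an assumed 3/10 versus 0/5 from 30.0 into 21.7 points.

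The missing rule at x = n does not depend on the reading. The same section recognises both boundaries for an arm's own rate and only one for the difference.

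Nothing confirmatory is at risk. The CMH p-values and the testing sequence do not use the substituted value, and comparisons with dupilumab at equal n show no shift. It would be wrong to infer bias in the co-primary tests, or an effect across all comparisons because of the 2:1 ratio, which applies only to a dose against placebo. The by-stratum, low-rate and subgroup figures rest on the assumed split, rates and sizes shown above.

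**What to change.** Amend SAP 5.2.1 to state that:

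- each proportion and the weighted difference are computed from the observed x/n;
- in the standard error only, p-hat is replaced by 0.5/(n+1) when x = 0 and by (n+0.5)/(n+1) when x = n;
- the same rule applies to the subgroup intervals in SAP 6.7.

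An acceptable alternative is a Miettinen-Nurminen interval (stratified for the main analyses), which handles both boundaries. The SAP already relies on the method elsewhere: "Tier-2 events will be analyzed using asymptotic methods proposed by Miettinen and Nurminen (1985").

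The cost is a few sentences of SAP text and a small programming change or standard software option. Trial conduct, data collection and the hypothesis tests are unaffected.

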- PF-04965842-matching orally administered placebo QD with dupilumab-matching subcutaneously injected placebo administered every other week (two injections at baseline; to dummy the loading dose) from Day 1 to Week 16 followed by orally administered 200 mg of PF-04965842 QD until Week 20.

Sample Size Determination

A total sample of 700 subjects, with 200 randomized to PF-04965842 200 mg QD, 200 subjects randomized to PF-04965842 100 mg QD, 200 subjects randomized to dupilumab and 50 subjects each randomized to two sequences of matching placebo for 16 weeks followed by (a) PF-04965842 100 mg QD and by (b) PF-04965842 200 mg QD (4:4:4:1:1 randomization) is planned. The two placebo sequences will be combined for purposes of analyses at all visits up to and including Week 16, which will result in a 2:2:2:1 randomization ratio. This will provide at least 96% power to detect a difference of at least 20% in IGA response rate between either dose of PF-04965842 and placebo, assuming the placebo response rate is 12% at Week 12. This will also provide at least 99% power to detect a difference of at least 30% in EASI-75 response rate between either dose of PF-04965842 and placebo, assuming the placebo response rate is 23% at Week 12.

Both co-primary endpoints must achieve statistical significance to meet the primary objective.

In addition, this sample size will also provide at least 92% power to detect a difference of at least 15% in the proportion of subjects with a ≥ 4 points improvement in the severity of Pruritus NRS between PF-04965842 and dupilumab, assuming the dupilumab response rate is 18% at Week 2.

The Type-I error rate is set at 5% (two-sided). The familywise Type-I error rate (for testing the co-primary and key secondary endpoints) will be strongly controlled at 5% using a closed-testing method based on a sequential, iterative Bonferroni-type approach. This is described in further detail in [Section 5.1](#).

The study has been sized to help gain sufficient safety data to be able to effectively evaluate the benefit-risk of PF-04965842 in conjunction with the other studies in the clinical development program, therefore the power for the co-primary endpoints is relatively high. This sample size will also help ensure adequate power is maintained for testing all the co-primary and key secondary endpoints for both doses of PF-04965842 via the multiple testing procedure.

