6.4. Secondary Efficacy Endpoints

6.4.1. Binary Endpoints

- Endpoints:
 - Weeks 2, 4 and 8 IGA, EASI-75 Response;
 - NRS4 for Severity Response each day from Days 2-15, Weeks 4, 8, 12 and 16;
 - Weeks 2, 4, 8, 12 and 16 EASI-50, EASI-90, EASI-100, SCORAD50, SCORAD75.
- Summary: Proportion of subjects with response at each specified time points;
- Population: FAS; Subjects from the FAS with a baseline NRS score for severity ≥ 4 will be used for NRS4 analysis;
- Statistical Method: CMH and normal approximation in [Section 5.2.1](#). P-value for PF-04965842 doses vs. dupilumab will also be presented for Days 2-15 NRS4;
- Missing Data: Missing data arising due to subject dropout are considered “non-response” (see [Section 5.3.1](#)).

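### The single-arm 95% intervals follow Wald except at 0% or 100%, which gives negative lower limits, an incoherent switch between 0 and 1 responder, and erratic coverage at low rates

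*SAP*

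**What the plan says.** SAP Section 5.2.1 sets the method for binary data at each scheduled visit. For each arm's own response rate: "The 95% confidence interval for the response rate in each treatment group will also be provided using Wald normal approximation", with one exception: "or the Clopper-Pearson exact method when there are no or all responders in one group". It does not provide for truncating limits at zero.

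The same section keeps inference separate: "p-values from the CMH statistic will be used to test the hypothesis of no difference in binary responses between two treatment groups". The treatment difference has its own CMH-weighted interval, in which an estimated proportion of zero is replaced by 0.5/(n+1).

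SAP Section 6.4.1 applies Section 5.2.1 to endpoints where few subjects may respond: IGA and EASI-75 at Weeks 2, 4 and 8, daily NRS4 from Day 2, and "Weeks 2, 4, 8, 12 and 16 EASI-50, EASI-90, EASI-100, SCORAD50, SCORAD75". Planned arm sizes (SAP Section 2.2) are 200 per active arm and 50 in each placebo sequence, and "The two placebo sequences will be combined for purposes of analyses at all visits up to and including Week 16", so placebo has n=100.

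**The concern.** The Wald interval is known to behave poorly when the expected number of responders is small. The SAP accepts this at exactly zero responders by switching method there, but reverts to Wald at the first responder, where the approximation is still weak. A single table could then show impossible limits, or an arm with one responder whose upper bound lies below that of an arm with none.

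At stake is whether the intervals printed beside the response rates mean what their 95% label says. No decision of the trial depends on them.

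**Working it through.** **The plan's own figures.** The SAP states no coverage beyond the nominal 95%. Its power figures confirm the arm sizes. For IGA (32% vs 12%, n=200 vs 100) the pooled rate is (64+12)/300 = 0.2533.
- Null SE = sqrt(0.2533 × 0.7467 × (1/200 + 1/100)) = 0.0533.
- Alternative SE = sqrt(0.32 × 0.68/200 + 0.12 × 0.88/100) = 0.0463.
- Power = Φ((0.20 - 1.96 × 0.0533)/0.0463) = Φ(2.06) = 98%, in line with "at least 96% power to detect a difference of at least 20% in IGA response rate".

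The same formula gives 99.95% for EASI-75 (stated: at least 99%) and 93.4% for NRS4 (stated: at least 92%).

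**Limits for small counts.** Wald is p̂ ± 1.96 × sqrt(p̂(1-p̂)/n). For 1/100: 0.01 ± 1.96 × sqrt(0.01 × 0.99/100) = 0.01 ± 0.0195. The Clopper-Pearson upper limit at x=0 is 1 - 0.025^(1/n), which is 3.62% at n=100 and 1.83% at n=200.

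| Responders | SAP rule | Wilson | Clopper-Pearson |
|---|---|---|---|
| 0/100 | 0 to 3.62% | – | 0 to 3.62% |
| 1/100 | -0.95 to 2.95% | 0.18 to 5.45% | 0.03 to 5.45% |
| 2/100 | -0.74 to 4.74% | 0.55 to 7.00% | 0.24 to 7.04% |
| 3/100 | -0.34 to 6.34% | 1.03 to 8.45% | 0.62 to 8.52% |
| 4/100 | 0.16 to 7.84% | 1.57 to 9.84% | 1.10 to 9.93% |

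At n=200 the lower limits for 1, 2 and 3 responders are -0.48%, -0.38% and -0.18%, and the upper limit falls from 1.83% at 0/200 to 1.48% at 1/200.

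**Coverage.** For a true rate p, coverage is the sum of the binomial probabilities P(X=x) over every x whose interval contains p. Rates from 0.5% to 10% are an assumed range. The rates 6.3% (Phase 2b placebo IGA, Protocol Section 1.2.4) and 12%, 18% and 23% (SAP Section 2.2) come from the documents.

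| True rate | SAP rule, n=100 | Wilson, n=100 | Clopper-Pearson, n=100 | SAP rule, n=200 |
|---|---|---|---|---|
| 0.5% | >99.9% | 91.0% | 98.6% | 99.9% |
| 1% | 99.9% | 92.1% | 98.2% | 99.9% |
| 1.5% | 99.9% | 93.6% | 98.2% | 84.8% |
| 2% | 99.9% | 94.9% | 98.5% | 90.8% |
| 3% | 85.0% | 96.9% | 98.9% | 93.3% |
| 4% | 90.6% | 93.6% | 96.4% | 89.8% |
| 5% | 87.7% | 96.6% | 98.3% | 92.6% |
| 6.3% | 94.5% | 96.5% | 96.5% | 93.2% |
| 8% | 89.6% | 96.0% | 97.5% | 95.3% |
| 10% | 93.2% | 93.6% | 95.6% | 92.7% |
| 12% | 94.9% | 95.7% | 97.0% | 94.0% |
| 18% | 94.4% | 95.0% | 96.3% | 94.4% |
| 23% | 95.3% | 95.8% | 95.8% | 94.4% |

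**Where the drop comes from.** At n=100 the Wald interval for one responder ends at 2.95%. Below that rate, x=0 and x=1 both cover, and coverage is above 99% (99.7% at 2.9%). At 3%, x=1 no longer covers and takes P(X=1) = 14.7% with it; the upper tail loses a further 0.3%, leaving 85.0%. At n=200 the same break comes at 1.48%. Above the break the misses are mostly in one direction: at 5% and n=100, 11.8 of the 12.3 percentage points missed come from intervals lying wholly below the true rate.

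**How often a negative limit would appear.** P(1 ≤ X ≤ 3) at n=100 is 62% at a true rate of 1%, 60% at 3%, 25% at 5%, 12% at 6.3% and 0.1% at 12%.

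**The case against.** The strongest defence is that the interval works where the documents let us check it. Coverage is 94.5% at 6.3%, 94.9% at 12% and 95.3% at 23% (n=100), and 94.4% at 18% (n=200). Neither document gives a rate for EASI-90, EASI-100, early IGA or early daily NRS4. If placebo EASI-100 were 2% or less, the SAP rule would be conservative. All of this stands.

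A reader might infer that these intervals under-cover badly at low response rates in general. They do not: the Clopper-Pearson switch at zero responders makes them over-cover at the lowest rates, and above the break coverage oscillates, so a single figure such as 85.0% is the bottom of a narrow dip.

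A reader might also infer that the trial's conclusions are affected. The documents do not support that either: p-values come from CMH, differences have a separate interval, and no test, multiplicity step or power figure uses the single-arm limits.

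Finally, a negative limit could be cut to zero for display. The SAP does not say so, and truncation would repair neither the coverage dip nor the fall in the upper limit between 0 and 1 responder.

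**Conclusion.** The point holds as a minor one. The negative limits for 1 to 3 responders and the incoherent switch follow from the rule as written, with no assumption about rates. The coverage shortfall is real but local: about 85% at worst, just above 3% (n=100) or 1.5% (n=200), then mostly 88-95% up to about 10%. Whether any arm meets it rests on the assumed range of 0.5-10% for the stricter and earlier endpoints. That range is plausible, since Phase 2b placebo IGA was only 6.3% at Week 12, but the documents do not state it. The intervals are descriptive, so the consequence is confined to how response rates are displayed and read.

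**What to change.** In SAP Section 5.2.1, name one method for the single-arm interval at every count and delete the switching rule. Either option removes the negative limits and the incoherent switch.

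- **Clopper-Pearson throughout** guarantees at least 95% coverage. The cost is width: for 12/100 it gives 6.36 to 20.02% (13.66 points) against 5.63 to 18.37% (12.74 points) for Wald.
- **Wilson throughout** is an acceptable alternative, narrower (7.00 to 19.81% for 12/100) and near 95% on average. It is not free of weakness: at n=100 it covers 91.0% at a rate of 0.5% and 92.1% at 1%.

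The change is one sentence and a software option, on the same data. No endpoint, test, multiplicity step or sample size changes.
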